13.3. Data and Safety Monitoring

Drs. [name] and [name] will conduct continuous review of study data and patient safety. The PI and Study Coordinator are responsible for continuously monitoring the conduct of the trial and are the primary individuals charged with identification and reporting of all AE and SAE occurrences. The review will include the number of patients, significant Pioglitazone toxicities as described in the protocol, and responses observed. The Investigator will submit summaries of this data at least annually to the Data Safety Monitor (DSM; see below) for review.

Additionally, a copy of the completed RSRB Annual Progress report will be submitted to DSM.

The Data Safety Monitor will be assigned oversight of safety monitoring and study progress. The DSM will review will review accrual and adverse events at least annually and following study completion. The DSM, [name], is a board-certified and practicing cardiologist who has experience with clinical trials.

All serious adverse events that the PI classifies as related or possibly related to therapy will be submitted to DSM for determination as to whether further action is required within 48 hours.

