2. STUDY DESIGN

2.1. Overview

This is a single center open label feasibility pilot project based at the University of Rochester. Patients followed in the University of Rochester Dermatology Clinic who have had between 2 to 6 squamous cell cancers treated in the past year, without contraindication for the use of Pioglitazone, and are on a stable drug treatment regimen will be offered participation. The study has a cross-over design, so patients will be enrolled and randomized in one arm of two treatment protocols: 1) six months of usual care while documenting and characterizing any new tumors that occur followed by 6 months of Pioglitazone treatment plus usual care for the next 6 months or 2) six months of Pioglitazone treatment followed by 6 months off treatment receiving usual care (see protocol diagram, Section 5, below). The second group will offer the opportunity to assess whether there is any persistent beneficial effect after pioglitazone treatment ends, while tumors from the first group that occur during the initial 6 months of usual care will be characterized by study parameters for comparison to tumors arising while on treatment. At the end of the one year treatment period, the number of new tumors that patients develop while taking Pioglitazone will be counted and compared with the number that patients developed during the 6 month period they were not receiving treatment as well as the numbers that occurred during the 6 months after treatment (washout effect). This information will be used as the basis for a larger multicenter study.

[figure not shown]

Fig 2. Schematic for the Proposed Study (study visit day are +/- 7 or 14 days)

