9.4. Responsibilities for Reporting Serious Adverse Events

The Investigator will record all serious adverse experiences that occur during the study period in the appropriate source documents and/or AE log as applicable. The study period for reporting serious adverse events will be from the time of signing consent to final study visit.

As sponsor of the relevant IND, the PI is responsible for compliance with the FDCA (21 USC §§ 301 e. seq.) as well as the implementing regulations [Title 21 of the CRF]. These responsibilities include reporting any unexpected fatal or life-threatening suspected adverse reactions to the FDA/CDER no later than 7 calendar days after initial receipt of the information.

Additionally, the PI will comply with all federal regulations and RSRB policies regarding the reporting of adverse events.

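### A serious adverse event that the PI judges unrelated need not reach the Data Safety Monitor until the at-least-annual review

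*Combined protocol and SAP*

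**What the plan says.** Section 13.3 makes the PI and the study coordinator the people who "are the primary individuals charged with identification and reporting of all AE and SAE occurrences". From them, information reaches the DSM in two ways.

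- **Prompt route.** Entry depends on the PI's view of causality: "All serious adverse events that the PI classifies as related or possibly related to therapy will be submitted to DSM". The same sentence closes by giving the purpose of this step and a time limit: "for determination as to whether further action is required within 48 hours".
- **Periodic route.** "The Investigator will submit summaries of this data at least annually to the Data Safety Monitor", and the DSM is to "review accrual and adverse events at least annually and following study completion". The DSM also receives a copy of the annual progress report to the review board (RSRB).

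The DSM "is a board-certified and practicing cardiologist who has experience with clinical trials". Section 9.4 adds a second role for the person who attributes events: "As sponsor of the relevant IND, the PI is responsible for compliance". Section 2.1 settles blinding: "This is a single center open label feasibility pilot project based at the University of Rochester".

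Section 9.4 also requires the Investigator to record all SAEs between consent and the final visit, but in source documents or the adverse event log. Its seven-day report goes to the FDA and is confined to unexpected fatal or life-threatening reactions that are suspected to be due to the drug.

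**The concern.** The causality opinion of one treatment-aware person decides whether an SAE goes promptly to the monitor or waits for a periodic summary. A call of unrelated is the one call that gets no prompt second look.

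This matters most for the heart. Section 10.1 lists worsening heart failure and fluid retention among the primary risks. Section 3.2 excludes only NYHA Class III or IV, and Section 2.3 expects some subjects with stage 1 or 2 heart failure. (Section 3.4 summarises heart failure as excluded, but the criterion itself is narrower.) In such a subject, a cardiac admission could be put down to the existing disease. The plan has appointed a cardiologist as monitor, yet does not require that person to see such an event promptly unless the PI first accepts at least a possible link.

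What is at stake is how soon someone outside the reporting line can see a pattern across subjects while others are still starting or taking the drug.

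**Working it through.** The plan states no figure for this point, so there is none to reproduce. The check is a comparison of sections plus simple arithmetic.

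**1. Is there any other prompt route to the DSM?**

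- Section 13.3, prompt route: needs a classification of related or possibly related.
- Section 13.3, summaries and DSM review: no causality condition on the adverse events reviewed, but the required frequency is at least annual.
- Section 13.3, continuous review by two physicians: nothing says that it forwards SAEs judged unrelated to the DSM.
- Section 9.4, recording: covers all SAEs, but sends none to the DSM.
- Section 9.4, FDA report: depends on a suspected relationship and goes to the FDA.
- Section 9.4, federal and RSRB rules: compliance is promised, but no route to the DSM is described.

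No section sends an SAE judged unrelated to the DSM sooner than the periodic review.

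**2. How long can it wait?** Section 13.1 puts the final on-treatment visit at 168 ± 14 days.

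- Longest planned exposure: 168 + 14 = 182 days.
- Share of a 365-day review interval: 182 / 365 = 49.9%.
- Longest wait, for an event just after an annual review: about 365 days.
- Average wait, assuming events fall evenly between annual reviews: 365 / 2 = 182.5 days, or about six months.

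A subject's whole drug period can therefore end before the DSM hears of the event.

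**3. Who is left exposed?** Section 5.2 drops a subject on a grade II clinical or laboratory abnormality and attaches no causality condition; Section 7 repeats the criterion. The affected subject is therefore covered. That rule does not inform the DSM, however, and Section 7 replaces withdrawn subjects, so recruitment to drug goes on. The residual risk lies with other and replacement subjects.

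**4. What would the change cost in reports?** Section 3.1 gives 40 subjects. The documents give no SAE rate. Assume that 10% to 30% have at least one SAE of any cause during the study:

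- 0.10 × 40 = 4 subjects
- 0.30 × 40 = 12 subjects

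This counts subjects with an SAE, on or off drug, and not reports. It sizes workload, not harm.

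**5. Can the harm be sized?** Not from the documents. As an illustration, let p be an assumed risk of a cardiac SAE per subject and m an assumed share of these called unrelated. The chance of at least one such event missing the prompt route among 40 subjects is 1 − (1 − pm)^40:

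- p = 2%, m = 10%: 1 − 0.998^40 = 8%
- p = 5%, m = 25%: 1 − 0.9875^40 = 40%
- p = 10%, m = 50%: 1 − 0.95^40 = 87%

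The range is too wide to support a claim about likelihood. The gap in step 1 does not depend on it.

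**The case against.** The case for leaving Section 13.3 alone has several parts.

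- **The filter is wide.** It takes in possibly related events, so the PI must rule out even a possible link. Section 5.2 names heart failure as a monitored safety endpoint and Section 10.1 as a primary risk, which makes an on-drug heart-failure admission one of the less likely events to be ruled out. This stands: the gap is real, but this example should not be presented as the typical case.
- **Open-label knowledge need not favour a call of unrelated.** A reader might infer that the PI's knowledge of treatment, or role as IND sponsor, biases attribution in that direction. The documents do not show this; knowing that a subject is on drug could equally prompt a call of possibly related. The point is only that the call goes unchecked for a time.
- **Other oversight exists.** Two physicians review data continuously, the annual interval is a minimum frequency, and the DSM also gets the RSRB report. All true, but earlier review is permitted rather than required, and none of these is a prompt route to the DSM.
- **The individual is protected.** The grade II stop rule applies whatever the attribution. This stands, and it narrows the concern to other subjects.
- **The setting is modest.** This is a 40-subject single-center pilot of an approved drug, with about six months of exposure. That supports a light fix, but it is not a reason to keep the filter when removing it costs so little.

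**Conclusion.** The concern holds as a gap in timing. Under Section 13.3 an SAE that the PI judges unrelated need not reach the DSM until the at-least-annual review: up to about 12 months later in the worst case, and about six months on average if events fall evenly between annual reviews, against at most 182 days on drug.

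Two stronger readings are tempting and should not be drawn. The first is that independent review is removed for these events, or that they might never reach the DSM because the data under review are described partly in terms of pioglitazone toxicities. Section 13.3 also says that the DSM reviews adverse events, with no limit to related ones, so review is delayed and not lost. The second is that the affected subject stays on drug because the DSM was not told. The stop rule in Sections 5.2 and 7 does not wait for the DSM.

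A related defect is that the 48 hours is ambiguous. As written, it could limit the submission, the DSM's determination or the action.

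The timing result rests on the stated exposure window and on annual reviews being held no more often than required. The probability that a delayed report would matter cannot be estimated from the documents. The validity of the primary comparison is unaffected. This is a cheap improvement to safety oversight.

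**What to change.** Replace the SAE sentence in Section 13.3 with a rule to this effect: every SAE from signing of consent to the final study visit is submitted to the DSM within 48 hours of the PI learning of it, accompanied by the PI's causality opinion and whether the subject was on or off drug at the time. State that the 48 hours governs submission; if a time limit on the DSM's determination is also wanted, give it separately. Leave the at-least-annual review as it is.

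The window matches the one in Section 9.4, so the events are already being recorded. The cost is a small number of extra reports: SAEs in 4 to 12 subjects in all under the assumed 10% to 30%, some of which would go to the DSM under the present rule anyway. Design, sample size and analysis do not change.

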14. INVESTIGATOR RESPONSIBILITIES

Adequate training and supervision of the study team will be ensured by the Principal Investigator as described below.

The PI will

- Provide copies of the protocol, consent and any other study related materials (including all other information relating to the preclinical and prior clinical experience) to all study personnel with delegated responsibilities for this study.
- Discuss all protocol materials and information with study staff to assure that they are adequately informed regarding Pioglitazone and conduct of the study.
- Assure that all study staff members are qualified by education, experience and training to perform their specific responsibilities.
- The Investigator will ensure appropriate documentation of compliance to the protocol, informed consent process and obtaining verbal or written consent on an ongoing basis, with written progress reporting quarterly.
- The Investigator (and study staff) will identify, report and manage potential conflicts of interest biannually.
- A delegation log to document activities that have been authorized by the Investigator to study staff and a training log to document necessary protocol training activities will be completed will be utilized as part of this process.

